4.6 Study Procedures: On the Day of Enrollment

Screening Assessments

- Record WHO mucositis grade.
- Brief Pain Inventory.
- ECOG/Zubrod Performance Status.
- Oral cavity digital image collection to evaluate mucositis will be done on the day of enrollment, treatment initiation, end of week 9 and then week 12.
- Physical examination (demonstrating no pre-existing mucositis).
- Record mucositis due to other causes (oral candidiasis, infections, trauma, etc.).
- OM pain data monitoring (VAS included in pain app).
- Review bloodwork, including CBC and CMP during clinic visits.
- Record type of calorie intake (normal, liquid, soft, parental/enteral).
- Report use of IV fluids for hydration.
- EKG.
- Urine drug screen.
- Pregnancy test for women of childbearing age.

4.7 Training for the Intervention

Study investigators and/or study coordinator will train subjects for use of devices (OM Pain App) and study procedures during treatment.

Study procedures as per study calendar will continue until treatment with the study drug regimen is started.

4.8 Study Procedures: After starting study drug regimen(Weeks 1–7)

These procedures must be completed weekly during the study. These will be recorded once the patient starts the drug regimen when radiation-induced mucositis pain VAS is greater than 4/10 on the BPI and pain app. The following procedures, such as MDASI and PROMIS® questionnaire administration, and adverse event evaluation, using CTCAE, will also be completed if the patient presents with radiation-induced mucositis pain (VAS \geq 4/10) on the day of enrollment.

- Record WHO mucositis grade.
- Brief Pain Inventory.
- ECOG/Zubrod Performance status.

- MD Anderson Symptom Inventory.
- PROMIS® cognition and GI questionnaires.
- Oral cavity digital image collection to evaluate mucositis will be done on the day of treatment initiation, the end of week 9, and then week 12.
- Record mucositis due to other causes (oral candidiasis, infections, trauma, etc.).
- Record adverse events, using CTCAE v.5.0.
- Record type of calorie intake (normal, liquid, soft, parental/enteral).
- Report use of IV fluids for hydration.
- OM Pain App data monitoring (VAS included in pain app).
- Review OM Pain App device usage and proper reporting.
- Review opioid log and record use of oral anesthetics, laxatives, and antiemetics at home. This data is currently being collected in a section of pain app. Patients average weekly VAS pain scores (question 3 of BPI questionnaire) because of radiation induced mucositis will also be documented in EMR during weekly clinic visits as per standard of care.

- Monitor opioid usage through WIPDMP,
- Review bloodwork, including CBC and CMP.
- EKG will be performed at screening, week 7 and 12 for patients on buprenorphine patch

If a subject stops radiation therapy prior to week 7, visits will remain on the same schedule, Subjects will need to come in for a weekly visit(s).

4.9 Study Procedures: Follow-up Period (Week 8–12 from start of radiation therapy)

End-of-Treatment Procedures

To be completed by the CRC between week 8 to week 12. Refer to the study calendar for details.

- Record WHO mucositis grade.
- Brief Pain Inventory.
- ECOG/Zubrod Performance status.
- Evaluate and record potential other causes of mucositis (oral candidiasis, aphthous ulcer, infections, trauma, etc.).
- PROMIS® GI and cognition questionnaires recorded over phone or in person weekly.
- MD Anderson Symptom Inventory recorded over the phone or in person weekly.
- Oral cavity digital image collection to evaluate mucositis will be done on the day of treatment initiation, the end of week 9, and then week 12.
- Physical examination (demonstrating no pre-existing mucositis).

- Record adverse events, using CTCAE v.5.0.
- Record type of calorie intake (normal, liquid, soft, parental/enteral).
- Report IV fluids for hydration.
- Review OM Pain App device usage and proper reporting.
- OM pain data monitoring (VAS included in pain app). Data from week 9 will be used for primary endpoint analysis.
- Review bloodwork, including CBC and CMP.
- Review opioid log and record use of oral anesthetics, laxatives, and antiemetics at home. This data is currently being collected in a section of pain app. Patients average weekly VAS pain scores (question 3 of BPI questionnaire) because of radiation induced mucositis will also be documented in EMR during weekly clinic visits as per standard of care.
- Monitor opioid usage through WIPDMP.
- EKG will be performed at screening, week 7 and 12 for patients on buprenorphine patch

4.10 Eligibility Confirmation

Study staff must adhere to MCWCC CTO SOPs regarding eligibility review/confirmation.

No waivers of protocol eligibility will be granted. When clinical factors relating to an eligibility item are unclear or questionable, the MCW PI can only provide guidance or clarification on eligibility. Any eligibility questions should be directed to [name] at [contact].

Study Population Locally advanced (stage I to IV) head and neck cancer patients being treated with either definitive or adjuvant radiation with or without chemotherapy who fulfill all eligibility criteria will be enrolled in this study. Patients deemed eligible for the study will be screened and enrolled in the study; treatment with study regimen will start once mucositis-related pain measured by VAS $\geq 4/10$ anytime during first six weeks of radiation therapy.

Inclusion Criteria

1. Age > 18 years.
2. Histologically confirmed malignancies of Head and Neck Stage I-IV by American Joint committee on cancer (AJCC) staging criteria 8th edition involving(oral cavity, oropharynx, nasal or paranasal sinuses, hypopharynx and larynx etc.) including both squamous and non-squamous cell histology's (salivary gland carcinomas and carcinomas of unknown primary will be included)
3. Undergoing a course of either definitive radiation (dose of at least 50 Gy to the head and neck region) with or without chemotherapy or adjuvant radiation (at least 50 Gy to the head and neck region) with or without chemotherapy. (Patients with a history of prior definitive course of radiation will be allowed).
4. ECOG Performance status ≤ 2 .
5. Concurrent enrollment on interventional trial is allowed.
6. English speaking and literate.
7. Patients will be allowed to take radiotherapy mix, viscous lidocaine or magic mouthwash-like agents that do not contain opioids. Tylenol® is allowed for fever or mild pain before starting drug regimen. It can be used for fever anytime during the study. Use of Tylenol for non-radiation mucositis related pain may be allowed in rare circumstances at investigators discretion.
8. Adequate organ function: Minor dose adjustments for tramadol are required in severe liver and renal impairment so we would only include patients with adequate organ function outlined in the table below. No dose adjustment for renal or hepatic impairment is required for TD buprenorphine. Some other parameters like hemoglobin, platelets and WBC are required for administration of standard of care chemotherapy like cisplatin along with radiation in treatment of HNSCC. They are not required for administration of buprenorphine or tramadol.

Organ Function Table	
Adequate hepatic function:	
total bilirubin	< 2 mg/dL
AST(SGOT)/ALT	< 5 times institutional upper limit
Adequate renal function:	

Organ Function Table	
creatinine clearance	> 30 mL/min/1.73 m ² for patients with creatinine levels above institutional normal

9. Pregnancy: It is known that standard-of-care treatments of HNSCC radiation therapy and chemotherapy have detrimental effects on human pregnancy or development of the embryo or fetus. Therefore, female patients participating in this study should avoid becoming pregnant, and male patients should avoid impregnating a female partner. Non-sterilized female patients of reproductive age and male patients should use effective methods of contraception through defined periods during and after study treatment as specified below.

Female patients must meet one of the following:

- Postmenopausal for at least one year before the screening visit, or
- Surgically sterile, or
- If they are of childbearing potential, agree to practice two effective methods of contraception from the time of signing of the informed consent form through three months after the last dose of study drug, AND
- Must also adhere to the guidelines of any treatment-specific pregnancy prevention program, if applicable, or
- Agree to practice true abstinence when this is in line with the preferred and usual lifestyle of the subject. (Periodic abstinence [e.g., calendar, ovulation, symptothermal, post ovulation methods] and withdrawal are not acceptable contraception methods.)

Male patients, even if surgically sterilized (i.e., status post-vasectomy), must agree to one of the following:

- Practice effective barrier contraception during the entire study treatment period and through 90 days after the last study drug dose, OR
- Must also adhere to the guidelines of any treatment-specific pregnancy prevention program, if applicable, OR
- Agree to practice true abstinence when this is in line with the preferred and usual lifestyle of the subject. (Periodic abstinence [e.g., calendar, ovulation, symptothermal, post ovulation methods] and withdrawal are not acceptable methods of contraception.)

10. Ability to understand a written informed consent document, and the willingness to sign it.
 11. Ability to operate and key in information on OM Pain App (a smartphone application).

Exclusion Criteria

A potential subject who meets any of the following exclusion criteria is ineligible to participate in the study.

1. Physical exam demonstrating pre-existing mucositis from prior radiotherapy treatments or other causes.
2. Pre-existing oral infection or ongoing toxicity from prior radiotherapy.
3. History of opioid abuse disorder, confirmed by medical history or subject disclosure. positive urine drug screen at screening visit. Exceptions will be made for subjects with current prescriptions post-surgery or other medical intervention.

4. Patients with multiple distant metastasis (patients with resectable oligometastasis will be allowed).
5. Current or recent use of short acting mixed opioid agonists/antagonists or other opioid antagonists. (Treatment with more than 2 doses of short acting oral or intravenous opioids like Oxycodone, morphine or hydromorphone within 24 hours of screening). Patients on treatment with long-acting opioids like fentanyl patch, methadone, oxycodone extended release, morphine extended release within 72 hours of screening would be excluded.
6. Prolonged QTc greater than 450 milliseconds in males and greater than 470 milliseconds in females at the time of enrollment
7. Patients on systemic therapy (chemotherapy or immunotherapy) for another cancer subtype.
8. Patients receiving induction chemotherapy prior to or after radiation/chemoradiation, such as patients with nasopharyngeal carcinoma.
9. Patients with a history of abdominal surgery within 60 days of registration, acute gastrointestinal conditions like colitis and appendicitis within four weeks of screening.
10. Patients with conditions that may compromise the blood-brain barrier permeability. The blood-brain barrier may become leaky in select neurological diseases, such as amyotrophic lateral sclerosis, epilepsy, brain trauma, and edema.
11. Patients presenting with any other cause of pain not related to radiation-induced mucositis or head and neck cancer, VAS >4/10 on BPI questionnaire (question 3: worst pain in last 24 hours) on the day of enrollment requiring opioid medications for pain control
12. Patients with a history of myocardial infarction ≤ 6 months prior to registration.
13. Patients with a history of significant respiratory depression; acute or severe bronchial asthma; known or suspected gastrointestinal obstruction, including paralytic ileus.
14. History of serious or severe hypersensitivity reaction to buprenorphine, tramadol or any of its excipients.
15. Use of the following drugs will not be permitted after initiation of study drug regimen: capsaicin, NSAIDS, tetrahydrocannabinol, and cannabinoids. Refer to Section 7 for details on contraindication of drug regimen. Patients will be allowed to participate in the study if they have been using antidepressants like SSRI'S, other antipsychotics and antiseizure medications for at least 4 weeks prior to enrollment on the study. Chronic use of these agents will not affect our primary endpoint of assessing impact of study regimen of Buprenorphine and Tramadol on alleviating acute radiation induced mucositis pain. As per package insert of buprenorphine and tramadol concomitant use of the above-mentioned agents with study pain regimen is not contraindicated. However, clinicians are advised to exercise caution as there have been some rare incidences of serotonin release syndrome (SRS) with concurrent administration of SSRI's and Tramadol. Buprenorphine is also not contraindicated but should be used with caution in patients with h/o seizure disorders. Study regimen can be stopped if SRS or any other adverse event occurs as a consequence of this combination. Periodic EKG's will also be performed to monitor for QTc prolongation.
16. Pregnant and lactating women are excluded from this study because chemotherapy and radiation given for the treatment of HNSCC have a potential for teratogenic or abortifacient effects. Additionally, buprenorphine is classified as category C for use during pregnancy, which means that the risk of adverse effects on the fetus cannot be ruled out. Buprenorphine does cross the placenta, and the use of opioids during pregnancy may result in neonatal withdrawals soon after birth. Symptoms of this may include irritability, apnea, increased tone, tremor, convulsions, or respiratory depression

Subject Initials: _____

Subject Study ID: _____

in the neonate. The onset of withdrawal in a neonate whose mother has taken buprenorphine during the pregnancy could be anywhere from the first day of life to the eighth day of life.

17. Patients with history of seizure disorder as oral tramadol may reduce seizure threshold.
18. Patient with history of opioid use disorder as defined by Diagnostic and Statistical Manual of Mental Disorders, 5th Edition. The Diagnostic and Statistical Manual of Mental Disorders, 5th Edition describes opioid use disorder as a problematic pattern of opioid use leading to problems or distress, with at least two of the following occurring within a 12-month period: 1. Taking larger amounts or taking drugs over a longer period than intended. 2. Persistent desire or unsuccessful efforts to cut down or control opioid use. 3. Spending a great deal of time obtaining or using the opioid or recovering from its effects. 4. Craving, or a strong desire or urge to use opioids 5. Problems fulfilling obligations at work, school or home. 6. Continued opioid use despite having recurring social or interpersonal problems. 7. Giving up or reducing activities because of opioid use. 8. Continued opioid use despite ongoing physical or psychological problem likely to have been caused or worsened by opioids. 9. Tolerance (i.e., need for increased amounts or diminished effect with continued use of the same amount) 10. Experiencing withdrawal (opioid withdrawal syndrome) or taking opioids (or a closely related substance) to relieve or avoid withdrawal symptoms.

"I have reviewed all inclusion/exclusion criteria and confirm the subject is eligible."	
CRC Name and Initials	Date
Enrolling Investigator Name (print)	
Enrolling Investigator Signature	Date

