	creatinine clearance	> 30 mL/min/1.73 m ² for patients with creatinine levels above institutional normal
Main Exclusion Criteria	
 1. Physical exam demonstrating pre-existing mucositis from prior radiotherapy treatments or other causes. 2. Pre-existing oral infection or ongoing toxicity from prior radiotherapy. History of opioid abuse disorder, confirmed by medical history or subject disclosure. positive urine drug screen at screening visit. Exceptions will be made for subjects with current prescriptions post-surgery or other medical intervention. Previous history of allergic reaction to buprenorphine and tramadol. 3. Patients with multiple distant metastasis. (Patients with resectable oligometastasis will be allowed). 4. Current or recent use of short or long acting mixed opioid agonists/antagonists or other opioid antagonists. (Treatment with more than 2 doses of short acting oral or intravenous opioids like Oxycodone, morphine or hydromorphone within 24 hours of screening). Patients on treatment with long-acting opioids like fentanyl patch, methadone, oxycodone extended release, morphine extended release within 72 hours of screening would be excluded. Patients presenting with any other cause of pain not related to radiation-induced mucositis or head and neck cancer VAS >4/10 on BPI questionnaire (question 3: worst pain in last 24 hours) on the day of enrollment requiring opioid medications for pain control. 5. Prolonged QTc greater than 450 milliseconds in males and greater than 470 milliseconds in females at the time of enrollment. 6. Patients receiving induction chemotherapy prior to or after radiation/chemoradiation; such as patients with nasopharyngeal carcinoma. 7. Patients with a history of abdominal surgery within 60 days of registration or acute gastrointestinal conditions, such as colitis and appendicitis within four weeks of registration. 8. Conditions that may compromise the blood-brain barrier permeability. The blood-brain barrier may become leaky in select neurological diseases, such as amyotrophic lateral sclerosis, epilepsy, brain trauma, and brain edema. 9. Patients with a history of myocardial infarction ≤ 6 months prior to registration. 10. Patients with a history of significant respiratory depression; acute or severe bronchial asthma; known or suspected gastrointestinal obstruction, including paralytic ileus. 	

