As noted earlier, radiation-induced mucositis begins to heal approximately two weeks after the last dose of stomatotoxic chemotherapy or radiation therapy.(30, 32) Hence, we will assess a percentage drop in pain score by the end of week 9 of treatment to show a drug response. This way we will be able to avoid any bias of the normal healing process on pain alleviation. Studies have also shown that painful mucositis continues four to five weeks after the termination of radiation therapy. Thus, we plan to continue the study drug regimen up to 12 weeks. (17) (32) Recording of data will cease after 12 weeks, at which time mucositis-related pain symptoms substantially abate in many individuals. Details on buprenorphine and tramadol dose determination and titration are included in Section 5.2 of this protocol. Post-marketing data of buprenorphine, other opioid studies, and clinical experience have shown that around 20 percent of the patients receiving transdermal buprenorphine may have inadequate pain control and require rescue off-protocol pain medications despite being on the highest titratable dose of buprenorphine. Therefore, we have allowed the use of oxycodone in situations where pain is uncontrolled on highest titratable doses of the drug regimen and plan to monitor the use off-protocol pain oxycodone in our study.(17, 34)

Details for the use and logistics of the OM Pain App, as well as the measure of the patient's compliance to the use of the pain app are detailed below. This study will not interfere with or cause adjustments to the standard-of-care treatments each patient will receive as determined by their multidisciplinary team of cancer doctors. To this end, basic treatment descriptions and standards are briefly described as a reference to ensure proper patient selection and to verify that patients observed on the trial will be somewhat homogeneous from a treatment perspective. A short description of possible supportive treatments that could be needed during treatment is also included. All study interventions and treatments will be administered on an outpatient basis.

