7.1.4 Contraindications

The only true contraindication to buprenorphine use is a hypersensitivity reaction to it. Its use requires caution in patients with respiratory depression, seizure disorder, and gastrointestinal obstruction. It should be avoided in patients with gastrointestinal obstruction and surgical abdomen, such as pancreatitis or appendicitis. Patients with significant respiratory depression, such as severe chronic COPD, asthma, or myasthenia gravis should not be given buprenorphine. Buprenorphine is also not a recommended agent for patients who are currently using full opioid agonists, such as heroin or morphine, because the concurrent use of a full and partial agonist may result in acute withdrawal (see "Monitoring"), thus, defeating the purpose of buprenorphine administration. Concurrent use of benzodiazepines, other CNS depressants and alcohol is prohibited. (42)

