7.2.4 Contraindications

- Patients who have previously demonstrated hypersensitivity to tramadol, any other component of this product or opioids.
- GI obstruction, surgical abdomen like pancreatitis or appendicitis.
- Patients with significant respiratory depression like severe chronic COPD/asthma or myasthenia gravis.
- Patients with acute or severe bronchial asthma or hypercapnia in unmonitored settings or the absence of resuscitative equipment.
- It also decreases seizure threshold by antagonizing 5HTc receptors.(47)
- All other opioid contraindications, including intoxication with alcohol, hypnotics, narcotics, centrally acting analgesics, opioids or psychotropic drugs.

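### Exclusion 14 admits patients with a past non-severe study-drug allergy, or hypersensitivity to another opioid, for whom Section 7 contraindicates a study drug

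*Combined protocol and SAP*

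**What the plan says.** The protocol states the hypersensitivity rule in four places.

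- Section 4.10, exclusion 14: "History of serious or severe hypersensitivity reaction to buprenorphine, tramadol or any of its excipients".
- Section 7.1.4, on buprenorphine: "The only true contraindication to buprenorphine use is a hypersensitivity reaction to it".
- Section 7.2.4, on tramadol: "Patients who have previously demonstrated hypersensitivity to tramadol, any other component of this product or opioids".
- Protocol Summary, Main Exclusion Criteria, within item 2: "Previous history of allergic reaction to buprenorphine and tramadol".

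Section 4.10 allows no eligibility waivers and ends with a statement, signed by the enrolling investigator, that all criteria were reviewed and the subject is eligible. It lets the principal investigator give guidance when clinical factors bearing on a criterion are unclear. Exclusion 15, within the same list, adds: "Refer to Section 7 for details on contraindication of drug regimen".

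**The concern.** The list that decides entry should be at least as strict as the contraindications the protocol itself states for its drugs. Here it is looser in two respects: it sets a severity threshold that Section 7 does not, and it omits the opioid class that 7.2.4 includes. An investigator could complete the list correctly and still start a patient on a drug that Section 7 says that patient should not have.

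The opioid-class gap also matters later in treatment. Table 2 in Section 5.4 lets the clinician replace tramadol with oxycodone, up to 90 mg a day, when pain persists on the highest doses. Section 5.1 expects that around 20 percent of patients may need rescue medication. Neither eligibility list screens out a patient with known hypersensitivity to oxycodone.

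What is at stake is participant safety and consistent application of the criteria, not the efficacy analysis.

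**Working it through.** No calculation bears on this point, so the check sets the texts side by side.

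| Source | Severity limit | Substances covered |
|---|---|---|
| 4.10, exclusion 14 | Serious or severe only | Buprenorphine, tramadol, excipients |
| 7.1.4 | None | Buprenorphine |
| 7.2.4 | None | Tramadol, its components, opioids |
| Synopsis, item 2 | None | Buprenorphine and tramadol |

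**Step 1: past non-severe allergic reaction to a study drug.** Exclusion 14 does not apply, because the reaction was neither serious nor severe. Section 7.1.4 contraindicates buprenorphine if that was the drug, and 7.2.4 contraindicates tramadol if that was the drug. The synopsis excludes the patient on a plain reading. (Read literally, its conjunction would require reactions to both drugs, which is unlikely to be meant.) The same patient is eligible in one place, excluded in another and contraindicated in a third.

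**Step 2: hypersensitivity to another opioid, of any degree.** Exclusion 14 does not name other opioids, and neither does the synopsis. Section 7.2.4 contraindicates tramadol. The patient passes both lists.

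**Step 3: severe reaction to an excipient of the buprenorphine patch.** On its natural reading, exclusion 14 excludes this patient. Section 7.1.4 and the synopsis do not mention excipients. On this aspect exclusion 14 is the wider rule.

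**Step 4: does the rest of the protocol settle the matter?** The Section 7 pointer sits in an item about drugs not permitted once treatment has begun. It does not turn the contraindications into exclusion criteria; if it did, the severity qualifier in exclusion 14 would have no effect. The clarification route covers unclear clinical facts. In steps 1 and 2 the clinical facts may be quite clear; it is the rules that differ.

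**Step 5: statistical reach.** The design in Section 8.4 does not depend on this criterion. Its rule of 10 or more responders among 18 gives an exact one-sided alpha of 0.0405 at 33% and power of 0.816 at 63%, in line with the stated 5% and 80%. Rewording exclusion 14 changes neither figure.

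**The case against.** The best defence is that the severity qualifier is deliberate. The rash guidance in Section 7.1.8 treats erythema and mild itching under the patch as common, manages a localized rash by moving the patch, and reserves stopping for severe reactions. Barring a patient for an earlier mild patch rash would make little sense. That is a fair reason for some threshold, but exclusion 14 does not state it, and the qualifier also covers tramadol, an oral tablet to which patch-site reactions are irrelevant.

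A second defence is that safeguards exist: the pointer in exclusion 15, the clarification route, the medical history taken at screening (4.4) and investigator supervision of dispensing (5.8). These do reduce the chance of harm. They do not tell the investigator which rule prevails. Nor does the synopsis's heading of main criteria explain the difference. A summary may leave out excipients, but here it is stricter on severity than the body.

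A reader might also infer that exclusion 13 wrongly omits hypercapnia, since 7.2.4 lists "Patients with acute or severe bronchial asthma or hypercapnia in unmonitored settings or the absence of resuscitative equipment" while exclusion 13 reads "Patients with a history of significant respiratory depression; acute or severe bronchial asthma; known or suspected gastrointestinal obstruction, including paralytic ileus". The documents do not support this as an error. The contraindication is conditional on the setting. Section 5.1 says "All study interventions and treatments will be administered on an outpatient basis", but nowhere equates that with an unmonitored setting. Significant respiratory depression, which 7.2.4 illustrates with severe chronic lung disease, already covers part of that group.

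**Conclusion.** The concern holds as a minor safety-consistency correction. Exclusion 14 is narrower than 7.1.4, 7.2.4 and the synopsis on severity, and narrower than 7.2.4 on opioid class. It would be wrong to infer that it is narrower throughout, because it is wider than 7.1.4 and the synopsis on excipients.

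No number of affected patients can be given. The documents report no frequency of past reactions to these drugs or to other opioids, so neither a count of patients at risk nor an estimate of lost accrual can be supported. Nor do the documents establish which text reflects the clinical intent, only that they cannot all govern. The conclusion rests on reading the synopsis as meaning either drug, and on treating the Section 7 pointer as advice rather than as an exclusion criterion. The endpoint, alpha and power are unaffected.

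**What to change.** Reword exclusion 14 along these lines: *history of hypersensitivity (allergic) reaction to buprenorphine, tramadol, other opioids or any excipient; mild local patch-site erythema or pruritus and ordinary opioid side effects do not count*. Align item 2 of the synopsis with it. The explicit exemption keeps the sensible part of the present threshold. If the clinical team does intend to admit patients with mild past reactions, amend 7.1.4 and 7.2.4 to say so instead; either way, one rule should stand.

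The cost is an amendment to one criterion and the synopsis, with review board approval. A few more screened patients may prove ineligible, in a number the documents do not allow one to estimate. Section 8.5 expects no screen failures but already plans to replace any that occur, so that 18 patients can be evaluated.
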